INDONESIA UNIVERSITY

THE EFFECT OF TETRAGONULA AFF TOLERANT PROPOLIS
ETHANOL EXTRACT. BUREAU OF ENDOMETRIOSIS LESI
GROWTH, APOPTOSIS ACTIVITY CHANGE AND NETWORK
ENDOMETRIOSIS ACTIVITIES

[figure not shown]
STUDY PROTOCOL

[name]

FACULTY OF MEDICINE
MEDICAL SCIENCE DOCTORAL PROGRAM

JAKARTA
AGUSTUS 2019

STUDY PLANNING

[figure not shown]
The study involved 80 endometriosis mice which were randomly divided into 16 distinct groups: the sham (SH) -0, SH-2, SH-4, SH-6, negative control (KN) -2, KN-4, KN groups -6, positive control (KP) -2, KP-4, KP-6, Dosage of Propolis 1 (P50) -2, P50-4, P50-6, Dosage Propolis 2 (P100) -2, P100-4, P100-6. All mice that will be made endometriosis models are certain to have a normal estrous cycle. The first laparotomy was performed to make an endometriosis model according to the Vivian technique, which was confirmed to be successful 30 days later with a second laparotomy. Subsequently given different treatment according to the study group and carried out a third laparotomy at the appropriate time (2, 4, and 6 weeks after the second laparotomy).

TREATMENT OF RAT

All rats were treated in the ARF IMERI FKUI laboratory. Standard care in research rate follows standard maintenance protocols according to Bauman¹³⁵ to provide optimal well-being for these rats, including: the need for social contact, a place to rest, a place to hide, exploration needs, the need for nutrition and free from environmental disturbances (e.g temperature, sound, etc.)

ESTRUS CYCLE EXAMINATION

The estrous cycle of rats was examined by taking vaginal lavage. Each rat in one cage was marked to distinguish the first to fifth mice. Vaginal discharge is taken by inserting the tip of a plastic pipette containing 10 μ L NaCl 0.9% into the rat's vagina, but not too deep. If the rat is considered aggressive, sampling can be carried out. The vaginal discharge is then placed on a glass slide. Glass slide that is used is different for each cage.

[figure not shown]

PROPOLIS ETANOL EXCRETION

Ethanol Propolis extract (EEP) is made from fine Propolis extracted with 96% ethanol using the method described in Pratami. EEP powder according to the treatment dose was dissolved in 10 cc of aqua before it was given to rat endometriosis models

1st LAPAROTOMY

[figure not shown]
1. Anaesthesia of rats (pentobarbital sodium, 50 mg / kg BW i.m.)
2. Perform Asepsis and antisepsis procedures in the abdomen of the rat
3. Incision mediana below the center along the 4 cm
4. Treat bleeding
5. Identification of bikornu uterus
6. Resection of rat uterus by 0.5 x 0.5 cm with regard to the endometrium and serous sides
7. Suturing the rat's uterus in the right anterior peritoneum 3 cm from the line
8. incision with the endometrial side facing the peritoneum
9. After there was no bleeding, the abdominal wall was covered in one layer with PGA thread number 2.0
10. Rat returned to the cage, then complete the research form

Bikornu Uterus Identification

Incision in the uterus

Stitching the uterus into peritoneum

2nd LAPAROTOMY

1. Anesthesia of rats
2. Perform Asepsis and antiseptic procedures in the abdomen of the rat
3. The median incision is below the center 4 cm long
4. Treat bleeding
5. After the peritoneum is opened, display the endometriosis lesions that have formed
6. Do lesion documentation
7. Excision of the formed lesion, then insert the tissue into the anatomic pathology tube
8. Cover the entire abdomen using a thread and complete the research form

THE TREATMENT

The treatment is given by sonde orally

PROPOLIS

Each milliliters contains 20mg of propolis. The propolis dosage that we use is 50mg/kg BW. So, we give 0,2ml for propolis 50 treatment, and 0,4ml for propolis 100 treatment

DIENOGEST

We use 0,1mg/Kg BW/day dienogest

WATER

We give 0,2 ml every day for each rat

SPECIMEN COLLECTION

After the treatment is done (for 2, 4, and 6 weeks), we do the necropsy. We take a picture of the lesion (to compare with the beginning lesion), then we take the lesion and peritoneal rinses and blood for the protein level examinations. We also take the ovarium, uterus and peritoneum for pathologic anatomy examination for each treatment.

SPECIMEN EXAMINATION

Protein Levels of Bax, Bcl, Cleaved Caspase 3, IL-1B, and PGE 2

Protein samples were obtained from endometriosis tissue taken by the treatment group. The lysis network uses a lysis buffer solution at 4 ° C for 30 minutes. The total protein is then broken down based on its molecular weight by the SDS-PAGE (Sodium Docecyl Sulphate-Polycramide Gel Electrophoresis) method and transferred to the PVDF (Polyvinylidene Difluoride) membrane. The membrane is then incubated with primary antibodies (Anti-Bax antibody [Abcam], Anti-Bcl-2 antibody [Abcam], Anti-Cleaved Caspase-3 antibody [Abcam], Anti-IL-1B antibody [Abcam]), followed by incubation with secondary antibodies (Horse-Radish Peroxidase [Santa Cruz Biotechnology]). Proteins that have been bound to antibodies are then viewed using enhanced chemiluminescent reagent kits [Boster Bio]

Molecular docking

Twenty-three compounds contained in Propolis were tested by screening using rule 5 (Lipinski's rule) consisting of: molecular weight <500 Dalton, <10 hydrogen donor bonds, <10 hydrogen acceptor bonds, partition coefficient values between -5 to 5. The screening results determine which compounds can enter the body and can work in endometriosis tissue. Furthermore, the three-dimensional shape is made of compounds which have passed the first stage. This process was created using the Marvin Sketch program. Furthermore, the compound that has been formed is stored as a ligand with extension pdb (protein data bank). Look for NFκB receptor proteins, estrogen A, estrogen B, progesterone A and progesterone B in the protein data bank, which will be stored as protein. Ligands and proteins are tested using standard Lamarckian algorithms in the Autodock program. The results obtained are in the form of bond energy (ΔG), where smaller results indicate a higher likelihood of interaction.

Examination of PGE2 receptor mRNA expression

Isolation of RNA in Endometriosis Tissue Samples

The RNA isolation process is carried out by first preparing a mixture consisting of 400 μL RB Buffer and 4 μL Beta-Mercaptoethanol. Then, the tissue is removed and placed in a later RNA, then the later RNA is removed and mixed with RB buffer and beta mercaptoethanol

RNA spectrophotometry

The instrument used to measure the concentration and purity of RNA is the Nano Drop Spectrophotometer. The device is turned on then the sample place is cleaned with tissue and distilled water. After that, blank measurements were taken by dripping RNase-free water as much as 2 μL in the sample place. Next, concentration and purity (A_{260} / A_{280}) measurements were taken in each sample. After the measurement is complete, the sample is again stored at -20 °C.

Synthesis of cDNA

CDNA synthesis was carried out using the ReverTra Ace[®] qPCR RT Master Mix kit with gDNA Remover [Toyobo] based on the ReverTra Ace[®] qPCR RT Master Mix Instruction Manual protocol with gDNA Remover (Toyobo 2017: 2). The first thing to do is calculate the ratio of the volume of RNA template and free water in order to obtain a mixture with a final concentration of RNA 25 ng / μL with the formula:

$$\text{Volume RNA} = \frac{25 \text{ ng} \times 6 \mu\text{L}}{\text{Initial RNA concentration}}$$

$$\text{Volume nuclease free water} = 6 \mu\text{l} - \text{RNA Volume Used}$$

RNA templates and reagents to be used are placed on ice and then thawed. After that, Genomic DNase I reaction solution is prepared according to the table

Composition of Genomic DNase I solution

Materials	Volume
4x DN Master Mix (50 µl 4X DN Master Mix dan 1 µl g DNA Remover)	2 µL
RNA template	Variabel
Nuclease free water	Variabel
Total Volume	8 µL

Genomic DNase I reaction solution was then incubated at 37 ° C for 5 minutes then immediately placed on ice. Then, the Reverse transcription solution is made according to the following table with the sample remaining on the ice:

Materials	Volume
RNA template	8 µL
5x R Master Mix II	2 µL
Total Volume	10 µL

Realtime PCR

Determination of Melting Temperature (T_m)

The primary melting temperature (T_m) is determined by the formula:

$$T_m = 2^{\circ}\text{C} (\text{A}+\text{T}) + 4^{\circ}\text{C} (\text{G}+\text{C})$$

A = Adenin, T = Thymine, G = Guanin, C = Sitosi

Quantitative Real-time PCR (Q-PCR) samples

Real-time PCR is done using the QuantBR SYBR Green PCR kit

Master Mix [Qiagen] is based on the QuantiTech® SYBR® Green PCR Handbook protocol (Qiagen 2011: 11). Samples and reagents to be used are prepared and then homogenized by spin down. After that, the correction mix is made according to the following table:

Mix-real time PCR reaction composition

Components	Volume
Nuclease free water	4,6 μ L
2x QuantiTect SYBR Green PCR Master Mix	7,5 μ L
Primer forward	0,45 μ L
Primer reverse	0,45 μ L
Template cDNA	2 μ L
Total Volume	15 μ L

The reaction mix is then put into a 0.2 ml tube and homogenized by spin down for a few seconds then put into the Techne Prime Pro 48 [Techne] PCR machine and set according to the following table:

Real-time PCR cycle

Steps	Time	Temperature
PCR initial activation step	15 menit	95°C
Denaturasi	15 detik	95°C
Annealing	30 detik	57°C
Ekstensi	30 detik	72°C
Jumlah siklus	40	

The results are then compared with standard curves and analyzed

DATA ANALYSIS

Data on lesion area of endometriosis tissue models, Bax / Bcl-2, Caspase 3, IL-1B, and PGE2 ratios obtained from In Vivo research are numerical data that will be processed using SPSS 20. The data will be presented in the average form if normal distribution or median if not normally distributed. The normality of distribution will be known through the Shapiro Wilk Test. Differences in endometriosis responses between dose and duration groups were performed with the Anova test (normal distribution) or Kruskal Wallis (abnormal distribution). Changes in estrous cycles between groups are known through the chi square test.

To find out the binding of EEP active compounds, it was carried out using the in silico test. Compounds are said to bind when the value of ΔG is less than zero or negative. From the binding compounds, path analysis will be carried out to determine the relationship of the bonds with receptors related to the pathophysiology of endometriosis.

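### The time of randomisation relative to model confirmation is not stated, and the lesion recorded at confirmation is used neither to balance groups of five nor in the analysis

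*Combined protocol and SAP*

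**What the plan says.** The STUDY PLANNING section opens with the allocation: "The study involved 80 endometriosis mice which were randomly divided into 16 distinct groups". Four of the 16 groups are sham. The other 12 are negative control, positive control and two propolis groups, each at 2, 4 and 6 weeks. The section then turns to the estrous check, in the future tense ("All mice that will be made endometriosis models are certain to have a normal estrous cycle"), and to the first laparotomy that creates the model, "which was confirmed to be successful 30 days later with a second laparotomy". Treatment follows: "Subsequently given different treatment according to the study group". No time of randomisation is given, and there is no rule for failed models, deaths or replacement.

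In the 2nd LAPAROTOMY section, step 6 is "Do lesion documentation" and step 7 is "Excision of the formed lesion, then insert the tissue into the anatomic pathology tube". The SPECIMEN COLLECTION section has the lesion photographed at necropsy for comparison with the one at the beginning. The DATA ANALYSIS section compares groups by ANOVA or Kruskal-Wallis and names no baseline term, stratum or block.

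**The concern.** Two things are at stake.

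- **Group size.** If all 16 groups are formed before the first laparotomy, a rat whose implant fails, or that dies before treatment, is lost from a group already fixed at five. The losses fall where chance puts them, and some groups may start treatment with three animals or fewer.
- **Starting lesion size.** The protocol records the lesion before treatment and refers back to it at necropsy, so it treats starting size as relevant. Neither the allocation nor the test uses it. With five animals per group, chance differences in starting size can be as large as an effect one would hope to see, and the planned test leaves that variation in the error term.

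**Working it through.** **The plan's own figure.** Groups listed: 4 sham + 3 + 3 + 3 + 3 = 16, and 80/16 = 5 per group. The 12 non-sham groups hold 12 × 5 = 60 animals. The figure reproduces. No power calculation, SD or loss rate is given.

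**When is randomisation?** The text can be read two ways.

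- *Early:* the allocation sentence comes first. The animals are then described as ones that will be made models. Sham groups are part of the same division; if sham means no implant (the protocol does not define it), sham status must be fixed before the first operation.
- *After confirmation:* the animals divided are called endometriosis mice, which could mean established models. That label also covers the sham animals, so it is weak evidence of timing.

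Early allocation is the more natural reading, but it is an inference.

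**Losses, if allocation is early.** Let f be the probability that a model animal is lost before treatment. The documents give no value; 5%, 10% and 20% are assumed, with independent losses and no replacement.

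P(a group keeps 4 or 5) = (1−f)^5 + 5f(1−f)^4, and P(some group of 12 has ≤3) = 1 − [that]^12.

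If survivors are instead spread evenly over the 12 groups after confirmation, a group of three or fewer arises only when fewer than 12 × 4 = 48 of the 60 survive: P(Binomial(60, 1−f) ≤ 47).

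| Assumed loss | P(one group ≤3) | Some group ≤3, early allocation | Some group ≤3, spread after confirmation |
|---|---|---|---|
| 5% | 0.023 | 24% | about 0% |
| 10% | 0.081 | 64% | 0.6% |
| 20% | 0.263 | 97% | 42% |

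The chance that all 12 groups keep five is (1−f)^60 = 4.6%, 0.2% and about 0%. It is the same under both orders if only 60 animals are implanted. Later randomisation makes groups more even; it does not supply animals.

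**Starting size, under either order.** Express lesion size in units of the between-rat SD, and take it as normal.

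- Simple allocation: SD of the difference between two group means = √(2/5) = 0.63. P(|difference| > 0.5) = 2[1 − Φ(0.5/0.632)] = 43%. P(|difference| > 1) = 2[1 − Φ(1/0.632)] = 11%.
- Largest minus smallest mean among the four model arms at one time point: above 1 SD in 39% of simulated allocations.
- All 60 animals ranked by size and randomised in five sets of 12 (simulation): SD of the difference about 0.21; above 0.5 SD about 2% of the time.

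The last line is the best case. Blocking in batches gains less. If each batch is exactly 12 animals, it forms a single block and ranking gains nothing.

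**What a covariate would add.** If starting and final area correlate at ρ, adjustment leaves about 1 − ρ² of the error variance: 0.91, 0.75 and 0.51 for assumed ρ of 0.3, 0.5 and 0.7. The documents give no ρ.

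**The case against.** The strongest case against runs as follows.

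- **Timing.** A reader might infer that the protocol randomises before confirmation and that its groups are therefore biased by post-allocation exclusions. The documents do not support this. No time is stated, and a figure in the planning section that may show the sequence is not available here. Even under early allocation, losses before treatment in the model groups cannot be caused by the treatment. Bias would need something further, such as unblinded exclusion or replacement, or sham-versus-model comparisons in which only model animals are selected on success. This objection stands.
- **Loss rates.** They are assumed. This stands, so the loss figures are conditional. At 20% loss, late randomisation still leaves a 42% chance of a group of three or fewer.
- **Chance imbalance.** Simple randomisation is unbiased, and the ANOVA error term already reflects variation in starting size. This stands too: blocking and adjustment buy precision, not validity. With five per group the gain can still be worth having.
- **Excision.** As written, step 7 of the second laparotomy removes the lesion that the allocation would balance. Until this is reconciled with the necropsy comparison, it is unknown how far starting size predicts the outcome. This limits the size of the benefit, but it does not explain why a recorded baseline goes unused.
- **Practicality.** The protocol asks for documentation, which need not mean a measured area. It also appears to house five to a cage ("Each rat in one cage was marked to distinguish the first to fifth mice"), so late randomisation may mean rehousing or cages with mixed treatments. Both are real costs.

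**Conclusion.** The point holds in a limited form. The protocol leaves open whether randomisation precedes or follows confirmation at day 30, and gives no rule for failed models or deaths. If allocation is early, as the text suggests, uneven groups are likely at moderate loss: 24%, 64% and 97% for a group of three or fewer at assumed losses of 5%, 10% and 20%. The cost is in evenness and precision. Neither bias nor early randomisation as an established fact should be read into it.

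What does not depend on timing or loss rate is that the lesion documented before treatment is used in neither allocation nor analysis. Two groups of five then differ in mean starting size with SD 0.63 of the between-rat SD, and by more than 0.5 SD 43% of the time. This assumes normal values and simple allocation. What it means for the results depends on the unreported correlation between starting and final size, and on resolving the excision step. It should be changed, but it does not by itself invalidate the comparison.

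**What to change.** 1. Reconcile step 7 of the 2nd LAPAROTOMY section (excision of the formed lesion) with the comparison to the beginning lesion in SPECIMEN COLLECTION. The gain from the remaining steps depends on this.
2. State when randomisation takes place and what happens to failed models and to deaths, before and after it.
3. Allocate in two steps. Assign sham or model before the first laparotomy (assuming sham means no implant). At the second laparotomy, randomise only confirmed model animals to the 12 arm-by-duration groups.
4. Rank confirmed animals by documented lesion area and randomise within sets of 12 of similar size, allowing the last set to be incomplete.
5. Include starting lesion area as a covariate in the lesion-area analysis. Kruskal-Wallis takes no covariate, so name in advance an adjusted alternative for non-normal data.

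**Cost.** One later randomisation step and a measured area from documentation already planned. Confirmed animals may have to be held and allocated in batches, which weakens the blocking. Cage housing must be considered; if cage has to be the block, randomise arms within cage and rely on the covariate for size. Late randomisation does not replace lost animals: to expect 60 confirmed models, 60/(1−f) must be implanted, which is 64, 67 or 75 at the assumed 5%, 10% or 20% loss. If that is not possible, the protocol should say that smaller groups are accepted.

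### 2nd LAPAROTOMY, step 7, as written removes the lesion before treatment, yet that lesion is later compared with its baseline and assayed; the two sections must be reconciled

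*Combined protocol and SAP*

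**What the plan says.** **Implant.** 1st LAPAROTOMY, step 6, describes one piece of tissue: "Resection of rat uterus by 0.5 x 0.5 cm with regard to the endometrium and serous sides". Steps 7 and 8 suture it at one site on the right anterior peritoneum.

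**Second laparotomy.** STUDY PLANNING places it 30 days later, to confirm that the model has taken; group treatment comes after it. In 2nd LAPAROTOMY, step 5 reads "After the peritoneum is opened, display the endometriosis lesions that have formed". Step 6 documents the lesion, step 7 is "Excision of the formed lesion, then insert the tissue into the anatomic pathology tube", and step 8 closes the abdomen.

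**After treatment.** SPECIMEN COLLECTION says: "After the treatment is done (for 2, 4, and 6 weeks), we do the necropsy". It continues: "We take a picture of the lesion (to compare with the beginning lesion), then we take the lesion", together with peritoneal rinses and blood, for protein levels. SPECIMEN EXAMINATION takes its protein samples from endometriosis tissue.

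**Analysis.** DATA ANALYSIS opens with "Data on lesion area of endometriosis tissue models" and goes on to the protein measures. The plan for the tests is "Differences in endometriosis responses between dose and duration groups were performed with the Anova test", or Kruskal-Wallis if the data are not normal. No change-from-baseline test is described.

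**Groups.** STUDY PLANNING lists 16 groups, among them "the sham (SH) -0, SH-2, SH-4, SH-6".

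**The concern.** Step 7 comes after the lesion is documented and before treatment. It carries no qualifier: nothing visible calls it partial, a biopsy, or confined to named groups, and no second implantation is described. An operator who follows it exactly removes the tissue whose later size and protein content are the study's outcomes.

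Two things are at stake. The first is the research question. Lesion growth is in the study title; if the lesion has been removed, whatever is found at 2, 4 or 6 weeks is residual or recurrent tissue. The second is the baseline. If only part is removed, the step 6 record describes a larger lesion than the one present when treatment begins, and no step records what is left.

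**Working it through.** This is mainly a check of consistency. The plan gives no excised amount and no figure to reproduce.

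**1. Sequence.** One piece implanted (1st LAPAROTOMY, steps 6 to 8); lesion documented (2nd LAPAROTOMY, step 6); lesion excised (step 7); abdomen closed (step 8); treatment; lesion photographed and collected (SPECIMEN COLLECTION). The lesion that the last stage needs has been taken out at step 7, with nothing described that would put another in its place.

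**2. Readings that the visible text leaves open.**
- *Whole lesion, every rat.* This is the literal reading. It contradicts SPECIMEN COLLECTION.
- *Part of the lesion.* This fits the purpose of confirming the model. Step 6, made before the cut, then overstates the lesion at treatment start.
- *Some animals only, for example SH-0.* SPECIMEN COLLECTION covers weeks 2, 4 and 6 only, so SH-0 has no other tissue-collection step. Step 6 would then be a sound baseline in all treated rats. Step 8, closure, fits this reading less well.
- *One of several lesions.* Step 5 uses the plural, although one implant is described. Step 6 would then serve as baseline only if each lesion is recorded separately.

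**3. Animals concerned.** Groups: SH 4 + KN 3 + KP 3 + P50 3 + P100 3 = 16. With equal allocation (assumed), 80/16 = 5 per group. Whole or partial excision in the KN, KP, P50 and P100 groups concerns 12 x 5 = 60 rats. Adding SH-2, SH-4 and SH-6, if those rats also carry a lesion, gives 15 x 5 = 75. Excision in SH-0 alone concerns 5 rats and no treated rat.

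**4. Baseline overstatement under partial excision.** If a fraction f is removed, the step 6 record exceeds the lesion left by f/(1 - f):
- f = 10%: 0.10/0.90 = 11%
- f = 25%: 0.25/0.75 = 33%
- f = 50%: 0.50/0.50 = 100%

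These fractions are assumptions. The calculation also infers that step 6 is the baseline for the photograph, which the plan does not state.

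**5. Effect on the between-group tests under partial excision.** Assume that final lesion area is proportional to the tissue left. Equal excision in all arms then leaves the ratio between arms unchanged: for an illustrative 40% reduction, 0.6(1 - f)/(1 - f) = 0.6. What remains is noise from unequal excision. Let f be uniform on (a, b) and independent of lesion size. Then SD = (b - a)/√12, mean left = 1 - (a + b)/2, and c = SD/mean left. With v the CV of lesion area itself, total CV = √(v² + c² + v²c²).

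| Removed (assumed) | SD | Mean left | c | v = 20% | v = 30% | v = 50% |
|---|---|---|---|---|---|---|
| 0-10% | 0.0289 | 0.950 | 3.0% | 20.2% | 30.2% | 50.1% |
| 0-25% | 0.0722 | 0.875 | 8.2% | 21.7% | 31.2% | 50.8% |
| 25-75% | 0.1443 | 0.500 | 28.9% | 35.6% | 42.5% | 59.5% |

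The added noise is negligible for a small biopsy and material only if large and variable amounts are cut away. All values of f and v are assumptions that show the range; none is an estimate for this study.

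**The case against.** The strongest reply is that the rest of the plan points away from complete removal. The second laparotomy exists to confirm the model, and sending tissue to pathology fits a confirmatory sample. A planner who meant to remove every lesion would not then plan to photograph and assay it. The English is loosely translated, so the definite article in step 7 is weak evidence of intent, and the study-plan figure, which is not shown, may hold the missing qualifier. This stands: complete excision in every rat is the least coherent reading.

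A second reply is that the baseline error reaches no described test, because DATA ANALYSIS plans comparisons between groups only. This also stands. The overstatement in item 4 affects the photographic comparison, and the between-group tests are touched only through unrecorded variation in the tissue left.

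A third is that every excised fraction and CV is assumed, and that tissue which regrows after cutting need not follow the proportional model. That is correct, and it is why no size is claimed.

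None of this removes the contradiction. The more likely readings are inferences, and step 7 is an operative instruction that supports none of them in words. Under the partial reading, the baseline still needs correction.

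**Conclusion.** The point holds as a contradiction between a stated operative step and the plan's own outcomes, and it should be fixed. Confidence is medium, because a figure that is not shown may settle the intent.

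The consequence depends on which reading is true:
- Excision in SH-0 only: nil for treated rats; only the wording is at fault.
- A small biopsy: small. The baseline in the photographic comparison is somewhat overstated, and the noise added to the group tests is negligible under the assumptions above.
- Large and variable partial excision: material noise in the group tests and a seriously overstated baseline.
- Whole lesion removed in treated rats: fundamental, because the study would then measure recurrence after excision.

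A reader might infer that the study cannot measure lesion growth at all, or that the excision biases the comparison of propolis with its controls. The documents support neither. The first needs complete removal, which the purpose of the second laparotomy makes unlikely. The second needs excision to differ systematically between arms, and nothing in the text suggests that it does.

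**What to change.** Reconcile step 7 of the 2nd laparotomy with SPECIMEN COLLECTION by stating whether all or part of the lesion is removed, and in which groups.

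Where lesion is left in place after a partial excision, define the beginning lesion as the lesion remaining when treatment starts, and record it after the excision.

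Only if the whole lesion is in fact removed in treated rats, describe the outcome as recurrence after excision, and drop the comparison with the beginning lesion.

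The cost is one or two sentences and at most one extra photograph during a laparotomy already planned. No extra animals are needed.

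### The propolis mg/kg labels are unsupported: each arm gets one fixed volume, which meets its label exactly only at 80 g (one administration per dose, 20 mg/mL in both arms), and no body weight or scaling rule is given

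*Combined protocol and SAP*

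**What the plan says.** Under THE TREATMENT, the propolis paragraph gives a concentration and a per-kg dose: "Each milliliters contains 20mg of propolis. The propolis dosage that we use is 50mg/kg BW". It then presents the volumes as following from these: "So, we give 0,2ml for propolis 50 treatment, and 0,4ml for propolis 100 treatment". The dose of 100 mg/kg is never written out. It is inferred from the P100 label and the doubled volume.

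STUDY PLANNING lists the propolis arms as "Dosage of Propolis 1 (P50) -2, P50-4, P50-6, Dosage Propolis 2 (P100) -2, P100-4, P100-6", which is six of the sixteen groups.

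Four other statements bear on the point:

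- PROPOLIS ETANOL EXCRETION, on preparation: "EEP powder according to the treatment dose was dissolved in 10 cc of aqua before it was given to rat endometriosis models". It gives neither an amount of powder nor an animal weight.
- 1st LAPAROTOMY, step 1, gives the anaesthetic per kg: "Anaesthesia of rats (pentobarbital sodium, 50 mg / kg BW i.m".
- The dienogest arm is also dosed per kg: "We use 0,1mg/Kg BW/day dienogest".
- The water arm has a fixed daily volume: "We give 0,2 ml every day for each rat".

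No propolis dosing frequency is stated. The readable text contains no body weight, weight range, weighing schedule or rule tying the propolis volume to weight. STUDY PLANNING calls the animals mice in one place ("The study involved 80 endometriosis mice which were randomly divided into 16 distinct groups"), while most other sections call them rats.

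**The concern.** A dose in mg/kg becomes a volume only through a body weight. The propolis paragraph goes from concentration and mg/kg straight to one volume per arm, so the step that would justify the volume is missing.

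If the text is followed as written, every animal in an arm receives the same number of milligrams. The mg/kg then varies inversely with weight, both between animals and within an animal whose weight changes during treatment. Because treatment lasts 2, 4 or 6 weeks, any steady weight change would also make average mg/kg exposure differ between duration groups that carry the same label.

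What is at stake is how the result is reported and reused. P50 and P100 are the test-article arms, and a reader cannot take an effective mg/kg dose from this text.

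**Working it through.** **Inputs.** Concentration c = 20 mg/mL, P50 dose 50 mg/kg, and volumes 0.2 and 0.4 mL all come from the propolis paragraph. The P100 dose of 100 mg/kg is inferred from the label. Two assumptions are needed: one administration per dose, and the same 20 mg/mL in both arms.

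**Reproducing the plan's figures.** Volume = (mg/kg × kg) / (mg/mL). The stated volumes cannot be reproduced because the weight is missing, so I solved backwards for it.

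- P50: 0.2 mL × 20 mg/mL = 4 mg; 4 / 50 = 0.080 kg.
- P100: 0.4 mL × 20 mg/mL = 8 mg; 8 / 100 = 0.080 kg.

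Both volumes point to the same weight, 80 g.

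**Rounding.** If the volumes were rounded to 0.1 mL, the weight used could have been 0.15 × 20 / 50 to 0.25 × 20 / 50 (60 to 100 g) for P50, and 0.35 × 20 / 100 to 0.45 × 20 / 100 (70 to 90 g) for P100. Both arms then fit 70 to 90 g.

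**Frequency.** If mg/kg means a daily dose and the volume is given twice or three times a day, the implied weight is 2 × 4 / 50 = 160 g or 3 × 4 / 50 = 240 g.

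**Distance from the label.** With one administration per dose, delivered / label = 80 g / W in both arms. It lies within 10% only for W from 80 / 1.1 = 72.7 g to 80 / 0.9 = 88.9 g.

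**Illustration.** The documents give no weight, so every weight below is assumed. The range runs to both sides of 80 g.

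| Assumed weight (g) | P50 volume delivers (mg/kg) | P100 volume delivers (mg/kg) | Share of label | Volumes needed, P50 / P100 (mL) |
|---|---|---|---|---|
| 40 | 100 | 200 | 200% | 0.1 / 0.2 |
| 80 | 50 | 100 | 100% | 0.2 / 0.4 |
| 150 | 26.7 | 53.3 | 53% | 0.375 / 0.75 |
| 200 | 20 | 40 | 40% | 0.5 / 1.0 |
| 250 | 16 | 32 | 32% | 0.625 / 1.25 |

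The last column uses 50 / 20 = 2.5 mL/kg and 100 / 20 = 5 mL/kg.

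**Drift.** This does not depend on starting weight. An assumed gain of 10% lowers mg/kg by 1 − 1/1.10 = 9.1%, and a gain of 25% lowers it by 1 − 1/1.25 = 20%. A loss of 10% raises it by 1/0.90 − 1 = 11.1%.

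**What is not touched.** The nominal ratio is 8 / 4 = 2 at equal weight. If the 80 animals are split equally, each group has 80 / 16 = 5, so the labels concern 6 × 5 = 30 animals.

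**The case against.** The strongest reply is that no stated calculation is wrong. Both volumes agree with one common weight, so this could be an input that was used but not written down. That is fair as far as it goes. But stating 80 g would explain the two volumes without making one volume correct for animals of other or changing weights.

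The 80 g figure is conditional. Once daily is the natural reading by analogy with the water and dienogest arms, but it is not stated for propolis, and other frequencies move the figure to 160 or 240 g. Rounding widens 80 g to 70 to 90 g. These points stand and limit the precision. On each of these readings one unstated weight is still needed, and the volume still does not scale.

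The preparation sentence could be read as a powder amount that varies with the dose. If concentration differed by arm, the milligram amounts and the 2:1 ratio would both change. However, that reading conflicts with the single concentration and doubled volume in the propolis paragraph.

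The per-kg anaesthetic and dienogest doses suggest that animals may have been weighed. Nothing links such a weight to the propolis volume. Figures are not shown and the research form is not reproduced, so the absence can be claimed only for the readable text.

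A reader with a typical adult rat in mind might infer that the animals were underdosed. The documents do not support this: they give no weight, they use both mice and rats, and dose and weight records are not available. A reader might also infer that the planned tests fail. They do not, because DATA ANALYSIS compares dose and duration as groups, by ANOVA or Kruskal-Wallis, and plans no model in mg/kg.

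**Conclusion.** The point holds, and it is worth fixing. A per-kg dose has been turned into one fixed volume per arm, and the readable text offers no weight or scaling rule that would keep the dose at its label. Given one administration per dose and 20 mg/mL in both arms, the labels are met exactly only at 80 g; away from that weight the delivered dose is 80 g / W of its label.

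The consequence is confined to the mg/kg labels of the six propolis groups and to any conclusion stated in mg/kg. The table and drift figures show how sensitive the labels are and are not evidence that any animal was misdosed. The regimen remains repeatable as 4 mg or 8 mg per administration, if the preparation was 20 mg/mL throughout.

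Confidence is high for the multiplication and for the missing link between weight and volume in the readable text. It is lower for 80 g as the weight that the authors had in mind.

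**What to change.** If dosing is still ahead:

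- Weigh each rat at the start of treatment and periodically after that.
- State the propolis frequency, and whether mg/kg means per administration or per day.
- Replace the single volumes with 2.5 mL/kg (P50) and 5 mL/kg (P100) of the 20 mg/mL solution. These rates assume one administration per dose; a daily dose given in parts would be divided accordingly.
- Set the water volume per kg as well, and state the rule.

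If fixed volumes were already given, report 4 mg or 8 mg divided by recorded body weight (mean and range), by arm and duration. If no weights exist, label the arms 4 mg and 8 mg per administration and drop the mg/kg labels.

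The cost is routine weighing and one derived variable. Gavage volumes rise in rats above 80 g (0.5 and 1.0 mL at an assumed 200 g) and fall below it (0.1 and 0.2 mL at an assumed 40 g). The reported mg/kg may differ from the current labels. The planned group tests need no change.
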